5 STUDY DESIGN AND POPULATION

HPN424-1001 is a Phase 1/2a, open-label, multicenter, safety and PK study of HPN424 in adults with histologically or cytologically confirmed adenocarcinoma of the prostate with progressive metastatic disease which, in the opinion of the Investigator, requires initiation of new treatment.

The study was designed to be divided into 2 parts: Dose Escalation and Dose Expansion, however the Dose Expansion portion of the study will not occur. Dose Expansion information in this SAP has been marked with a ~~strikethrough~~ to indicate that it will not occur.

[figure not shown]
As an added safety measure for this first in human (FIH) trial, single patient cohorts will initially be enrolled and treated. Dose Escalation will then proceed following a 3+3 design to evaluate 2 treatment arms in parallel:

- Fixed Dosing
- Step Dosing

During single patient dose escalation and in the 3 + 3 dose escalation Fixed Dosing arm, patients will receive the Target Dose (the intended dose for a particular cohort) throughout the treatment period. Patients in the Step Dosing arm will initiate treatment with one (or more) Priming Dose(s) followed by the Target Dose level for the duration of treatment.

HPN424-1001 Study Design

Dose Escalation

HPN424 administered weekly by IV infusion or SC injection

Abbreviations: DLT = dose-limiting toxicity (per protocol); MTD = maximum tolerated dose; RP2D = recommended Phase 2 dose; toxicity = AEs related or suspected to be related to HPN424, except those judged not to present safety risk

For each treatment arm, Dose Escalation will continue until the MTD is declared, RP2D(s) are identified, or the Sponsor decides to stop enrollment in one or more arms. A Cohort Review Committee (CRC) comprised of selected Investigators and Sponsor representatives including the

Medical Monitor will monitor safety throughout the trial. Following completion of the DLT period for all patients in a given dose cohort, the CRC will review the safety, clinical activity, and any available PK and pharmacodynamic data prior to opening the next higher dose level.

During Dose Escalation, additional patients may be enrolled and treated at dose levels previously determined to be safe by the CRC, ie, backfilling previously cleared dose levels, after review and approval by the Sponsor. For example, these backfill cohorts may explore intermediate or lower dose levels, different priming dose levels, different schedules (e.g., split-dosing), or modified premedication use based on emergent safety and available PK data.

Patients actively receiving therapy may be considered for intra-patient dose escalation to receive a dose level no higher than the highest dose that has previously been deemed safe and tolerable (and thus below the MTD) by the CRC, following review and approval by the Medical Monitor.

HPN424 will be administered by either intravenous (IV) infusion or subcutaneous (SC) injection. All patients will be administered HPN424 once weekly (QW) during 21-day cycles. Pre-medications will be administered as indicated based on assigned cohort.

Patients may continue to receive HPN424 treatment beyond disease progression provided there is clinical benefit (NLCB, per PCWG3 guidelines) as determined by the Investigator and upon consultation with the Medical Monitor. Disease assessments (PSA, bone scans and CT/MRI) should continue irrespective of whether study treatment is missed or delayed.

5.1 Schedule of Assessments

Patient participation includes Screening (28 days), Treatment (ongoing in 21-day cycles), an End of Treatment visit (within 7 days after the last dose of HPN424), and Safety Follow-up (SFU; ≥ 28 days [+7 days] after the last dose of HPN424), after which patients will enter long term follow-up (LTFU) for survival. Patients may continue weekly HPN424 treatment as long as they are receiving clinical benefit (as determined by the Principal Investigator and upon consultation with the Sponsor Medical Monitor).

Schedules of visits and assessments conducted throughout the study are dependent on the assigned dosing regimen and route of administration, and are detailed in the following protocol appendices:

- Appendix 1: Fixed Dose Intravenous Regimen
- Appendix 2: Step Dosing Intravenous Regimen
- Appendix 3: Fixed Dose Subcutaneous Regimen

5.2 Sample Size Determination

Up to 150 patients with mCRPC may be enrolled. The number of cohorts and patients will depend on data observed during Dose Escalation.

Dose Escalation may include up to 130 patients, depending on the dose at which the MTD and RP2D(s) are determined. The sample size and design of the Dose Escalation portion of the study are consistent with those in other oncology studies used to determine MTD. The traditional 3 + 3

dose escalation scheme employs the standard NCI definition of MTD (highest dose associated with DLT in <33.3% of patients) for each arm.

~~Dose Expansion will include up to 20 evaluable patients using a Simon 2 stage design to assess preliminary clinical efficacy of HPN424 at the RP2D(s). Power calculations based on a Simon 2 stage minimax design test the null hypothesis that overall response rate (ORR) ≤ 0.01 versus the alternative hypothesis that ORR ≥ 0.15 , with a Type 1 error rate of 0.05 and power of 80%. This design would allow identification of a target response rate of 15% or better in a population of patients who have failed standard available therapy and would not be expected to have any responders.~~

~~A sample size of 14 evaluable patients will be enrolled in the first stage. If the total number responding (defined as partial response [PR] or complete response [CR] is ≥ 1 , an additional 6 evaluable patients will be enrolled in the second stage for a total of 20 evaluable patients. If the total number responding is ≤ 1 , the effectiveness of treatment based on ORR will be rejected. If treatment is actually not effective and ORR ≤ 0.01 , then the expected sample size is 14.8 evaluable patients with a 0.869 probability of early termination and there is a 0.016 probability of incorrectly concluding the treatment is effective (the target for this Type 1 error rate was 0.05 or less). If the treatment is actually effective, there is a 0.199 probability of incorrectly concluding it is not effective (the target for this Type 2 error rate was 0.20 or less).~~

~~While the intention is to study a single RP2D, additional expansion cohorts of up to 20 patients per expansion cohort may be added at the recommendation of the CRC. If the CRC recommends multiple RP2Ds, each will be evaluated with independent Simon 2 stage designs of up to 20 evaluable patients per RP2D.~~

5.3 Interim Analysis

No formal interim analyses are described in the protocol and none are planned. In Part 1, all available data will be reviewed to enable dose-escalation and dose selection decisions. Except for the occurrence of a MTD, there are no stopping rules described in the protocol.

A review of safety data, clinical activity, and any available PK and pharmacodynamics data will be conducted upon completion of each dose escalation cohort by the Cohort Review Committee (CRC). Additionally, a Study Safety Oversight Committee (SSOC) will review safety quarterly, including at the identification of any DLT, and will make recommendations to the CRC.

5.4 Timing of Analyses

~~Part 2 Dose Expansion of the study will be conducted in up to 2 stages. After testing the treatment on 14 evaluable patients in the first stage, the data will be analyzed and the study will be terminated if no (0) patients have a response (CR or PR). If at least 1 patient responds, an additional 6 evaluable patients will be enrolled in the second stage for a total of 20 evaluable patients.~~

~~The primary analysis will be conducted after all patients have completed at least 6 cycles of treatment or discontinued study treatment and completed the End of Treatment visit. A~~

~~supplemental analysis may be completed at the end of study that includes the cumulative data collected after the final analysis (i.e., through SFU).~~

On 10 March 2022, Harpoon Therapeutics decided to discontinue the study during Part 1 (dose escalation). Part 2 (dose expansion) of the study was not initiated. The clinical study report will be a synoptic report focusing on safety data. This sSAP describes the original study objectives and study endpoints but will not summarize any efficacy data, which will only be reported in by-patient listings.

5.5 Sources of Data

Data management of this study is being conducted with a contract research organization (CRO) using Medidata RAVE electronic data capture (EDC). All data management activities are handled under the SOPs of the CRO.

Protocol deviations were provided by Clinical Research from the clinical trial management system (CTMS).

Adverse event data is reported from the EDC only. The SAE database was used to reconcile the EDC adverse event database but is not included in any analyses.

6 DATA ANALYSIS CONSIDERATIONS

All analyses will be conducted using SAS® version 9.4 or higher.

All relevant clinical data collected in the electronic data capture (EDC) database will be presented in by-patient data listings, including any derived fields used in analyses. All listings will be sorted by study part, cohort, patient ID, and assessment date (and time, if available).

Descriptive summaries of continuous data will generally include the number of patients, mean, median, standard deviation, and minimum and maximum values. Descriptive summaries of categorical data will generally include the number of patients, count, and percentage based on the number of non-missing values. If one or more patients are missing data, the number of missing values will be presented as a separate category with no percentage. Counts of 0 will be presented without percentages.

No p-values will be derived for this Phase 1/2a study.

Data will be reported with the following precision:

- Mean, median: 1 additional decimal place to that reported in raw data
- Standard deviation: 2 additional decimal places to that reported in raw data
- 95% CIs: 2 additional decimal places to that reported in raw data
- Minimum, maximum: same precision to that reported in raw data
- Percentages: 1 decimal place

Patients who withdraw or are lost to follow-up will be included in statistical analyses to the point of their last evaluation.

6.1 Randomization and Blinding

This is not a randomized study. All study treatment will be administered open-label. Study patients, study center personnel, and Harpoon will not be blinded to study treatment or clinical data.

6.2 Stratification and Covariates

No stratification is planned for this study, and no covariate-adjusted analyses will be performed.

6.3 Analysis Sets

Patients will be summarized based on their assigned dose cohort. The following analysis sets will be used for this study:

- ***Safety Population:*** All enrolled patients who receive any amount of HPN424 study treatment.

6.4 Evaluation of Subgroups

No subgroup analyses are planned.

6.5 Multiple Comparisons and Multiplicity

The statistical analyses of data are descriptive in nature. Therefore, no adjustments for multiple comparisons or multiplicity are planned.

7 GENERAL DATA HANDLING CONVENTIONS

7.1 Data Display Characteristics

All data collected in EDC will be reported in by-patient data listings, including any derived variables. They will be sorted by cohort, patient number, and date/time of assessment. The data will include all patients in the database regardless of their receipt of study drug.

Part 1 of the trial has too many dose cohorts to reasonably fit on a single summary table. Since the primary goal of data review and reporting will be focusing on the major differences in dosing schedule, the goal will be to group the dose escalation cohorts. As a result, the following groupings of data will apply to table headers to summarize data in all demographic and safety tables:

- Fixed dose IV cohorts (cohorts 1 – 12)
- Step-dosing IV cohorts who received a single prime followed by the target dose (step cohorts 1, 301, and 302)
- Step-dosing IV cohorts who received two prime doses followed by the target dose (step cohorts 501 – 504)
- Fixed dose SC cohorts (cohort 701)

Summary tables will generally present the dosing cohorts as shown below.

Safety Tables

Parameter	Fixed IV	1 Prime Step IV	2 Prime Step IV	Fixed SC	Study Total
-----------	----------	-----------------	-----------------	----------	-------------

Specific study cohorts and treatment dose levels are as follows:

Study Part	Cohort Number	HPN424 Dose Levels
Dose Escalation Fixed Dosing IV	1	1.3 ng/kg IV
	2	4 ng/kg IV
	3	12 ng/kg IV
	4	24 ng/kg IV
	5	30 ng/kg IV
	6	40 ng/kg IV
	7	54 ng/kg IV
	8	72 ng/kg IV
	9	96 ng/kg IV
	10	120 ng/kg IV
	11	160 ng/kg IV
	12	150 ng/kg IV
Dose Escalation 1 Prime	1	12 / 36 ng/kg IV
	301	100 / 300 ng/kg IV

Study Part	Cohort Number	HPN424 Dose Levels
Step Dosing IV	302	75 / 225 ng/kg IV
Dose Escalation 2 Prime	501	100 / 300 / 450 ng/kg IV
	502	50 / 150 / 300 ng/kg IV (prior chemo)
	503	50 / 150 / 300 ng/kg IV (no prior chemo)
	504	50 / 150 / 450 ng/kg IV
Dose Escalation Fixed Dose SC	701	120 ng SC

Patients will be reported in their original dose cohort, regardless of any intra-patient dose escalation or dose changes. No patient on study received both IV and SC dosing.

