4.3 Primary Endpoints

Dose Escalation:

Number and severity of dose limiting toxicities (DLTs) following treatment with escalating doses of HPN424.

Dose Expansion:

~~Overall response rate (ORR), as assessed by PCWG3 criteria for response.~~

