10 SAFETY

All safety analyses will be based on the Safety Population.

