10.2 Adverse Events

Verbatim AE terms will be coded based using the Medical Dictionary for Regulatory Activities (MedDRA) Version 24.0 for reporting by System Organ Class (SOC) and Preferred Term (PT). The MedDRA version number will be reported in footnotes on each AE table and described in the study report.

The severity of AEs is graded by the Investigator according to the NCI CTCAE version 5.0, with the exception of CRS, which was graded by ASTCT criteria.

Treatment-emergent adverse events (TEAEs) are defined as all events that occur or worsen in severity during or after the first HPN424 study drug administration through 28 days after the last dose of study drug. In addition, any event that occurs after this time period is reported as a TEAE if the event is assessed by the investigator as related to study drug.

An overall summary of TEAEs will be provided that includes the patient incidences (numbers and percentages) by cohort and overall of the following categories of events:

- TEAEs
- TEAEs related to study drug
- NCI CTCAE Grade 3 or higher TEAEs
- NCI CTCAE Grade 3 or higher TEAEs related to study drug
- Treatment-emergent SAEs
- Treatment-emergent SAEs related to study drug
- Dose limiting toxicities (DLTs)
- CRS or IRR TEAEs
- TEAEs that lead to study drug discontinuation
- TEAEs related to study drug that lead to study drug discontinuation
- TEAEs that lead to dose reduction or interruption
- TEAEs related to study drug that lead to dose reduction or interruption
- Fatal TEAEs
- Fatal TEAEs related to study drug

The patient incidence by cohort of each of the above categories of TEAEs will be summarized separately by SOC and PT. Multiple TEAEs will be counted once per patient within each SOC and each PT. For TEAE summaries, multiple TEAEs will be counted once per patient at the

maximum severity NCI CTCAE grade reported within each SOC and each PT. Tables will be sorted by SOC and PT frequency in descending order of overall incidence.

An additional patient incidence summary will be provided sorted by PT showing TEAEs with an overall patient incidence rate > 10%.

Non treatment-emergent adverse events will be included only in the by-patient data listings.

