14.3.2.14	Summary of Treatment Emergent Adverse Events Related to HPN424 That Lead to HPN424 Dose Modifications by System Organ Class and Preferred Term
14.3.2.15	Summary of Dose Limiting Toxicity (DLT) Adverse Events by System Organ Class and Preferred Term
14.3.2.16	Summary of CRS Signs and Symptoms by Preferred Term (From CRS Symptom CRF)
14.3.2.17	Summary of IRR Signs and Symptoms by Preferred Term (From CRS Symptom CRF)

Table Number	Description
14.3.3	Summary of Deaths
14.3.4.1	Safety Laboratory Assessment Shift Table – Serum Chemistry Change from Baseline to Maximum Post-Baseline NCI CTCAE Grade
14.3.4.2	Safety Laboratory Assessment Shift Table – Hematology Change from Baseline to Maximum Post-Baseline NCI CTCAE Grade
14.3.4.3	Safety Laboratory Assessment Shift Table – Coagulation Change from Baseline to Maximum Post-Baseline NCI CTCAE Grade
14.3.4.4	Safety Laboratory Assessment Summary of Patients with Post-Baseline NCI CTCAE Grade 3 or Higher
14.3.5	Summary of 12-Lead Electrocardiogram Abnormalities and Potential QTcF Interval Prolongation
14.3.6	Study Drug Exposure and Compliance

Table of Contents - Listings

Listing Number	Description
16.2.1	Patient Disposition
16.2.2	Patient Enrollment and Eligibility (Inclusion / Exclusion)
16.2.3	Protocol Deviations
16.2.4.1	Demographics
16.2.4.2	Prostate Cancer Medical History
16.2.4.3	Prior Anticancer Therapy
16.2.4.4	Prior Radiation Therapy
16.2.4.5	Prior Prostate Cancer-related Surgery
16.2.4.6	Medical History
16.2.5.1	HPN424 Administration
16.2.5.2	HPN424 Infusion Interruptions
16.2.5.3	Hospital Admission
16.2.6.1	Overall Efficacy Endpoints
16.2.6.2	Radiographic Scans
16.2.6.3	Target Lesions
16.2.6.4	Non-target Lesions
16.2.6.5	New Lesions
16.2.6.6	Bone Scan Assessment
16.2.6.7	Overall Disease Assessment

Listing Number	Description
16.2.6.8	PSA Results
16.2.7.1	Adverse Events
16.2.7.2	Serious Adverse Events
16.2.7.3	Dose-limiting Toxicities
16.2.7.4	Adverse Events Leading to Treatment Discontinuation
16.2.7.5	Adverse Events Leading to HPN424 Dose Modifications
16.2.7.6	Fatal Adverse Events
16.2.7.7	Cytokine Release Syndrome / Infusion Related Reactions Symptoms
16.2.7.8	Deaths
16.2.8.1	Laboratory Results: Hematology
16.2.8.2	Laboratory Results: Chemistry and Testosterone
16.2.8.3	Laboratory Results: Coagulation
16.2.8.4	Laboratory Results: Urinalysis
16.2.8.5	NCI CTCAE Grade 3 or Higher Laboratory Results
16.2.8.6	Patients who had laboratory values that Meet Criteria for Hy's Law

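### SAP 7.1 pools 20 dose cohorts into four columns, including in the only dedicated DLT table, so the one retained primary endpoint is not clearly tabulated by dose level or regimen.

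*SAP*

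**What the plan says.** The primary endpoint that survives in SAP 4.3 is "Number and severity of dose limiting toxicities (DLTs) following treatment with escalating doses of HPN424". The expansion endpoint is struck out, and estimating the MTD or MAD stays as the Part 1 primary objective in SAP 4.1.

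SAP 7.1 explains that Part 1 has too many cohorts for one table and that the main interest is dosing schedule. It then rules that "the following groupings of data will apply to table headers to summarize data in all demographic and safety tables": Fixed IV (cohorts 1 to 12), one-prime Step IV (cohorts 1, 301, 302), two-prime Step IV (501 to 504) and Fixed SC (701). A Study Total column is added. It continues: "Summary tables will generally present the dosing cohorts as shown below".

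SAP 13.1 plans one table devoted to DLTs, 14.3.2.15: "Summary of Dose Limiting Toxicity (DLT) Adverse Events by System Organ Class and Preferred Term". DLTs are also one line of the overall TEAE summary, 14.3.2.1. The listing is 16.2.7.3, and 7.1 sorts listings by cohort. No planned table title refers to dose level or regimen.

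Two other places point towards cohorts. SAP 6.3 says patients are summarised by the dose cohort they were assigned to. SAP 10.2, whose categories include DLTs, says: "The patient incidence by cohort of each of the above categories of TEAEs will be summarized separately by SOC and PT".

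On denominators, "All safety analyses will be based on the Safety Population", and that population is "All enrolled patients who receive any amount of HPN424 study treatment". Protocol 3.1.1.2 instead states the MTD over DLT-evaluable patients. Protocol 5.2 allows patients with fewer than 3 Target doses, for reasons other than a DLT, to be treated as not evaluable.

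**The concern.** A primary endpoint about toxicity as dose rises needs a display in which dose can be seen. The grouping keeps route and number of priming doses and removes dose level, and for Step dosing it removes the priming sequence as well. A reader of the synoptic report could not tell from the DLT table whether events fell in one cohort or were spread over several. The reader also could not tell whether they came at the top of the dose range or lower down.

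The listing keeps the events but not the number of patients at risk. To recover a DLT count over a denominator for any cohort, the reader would have to cross-count DLT listing 16.2.7.3 against the dosing listing, 16.2.5.1. What is at stake is the readability of the answer to the trial's main remaining question, not the conduct of the escalation.

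**Working it through.** **1. The plan's own figure.** Protocol 3.1.1.2 gives the MTD rule as DLTs in fewer than 33% of evaluable patients, equated to fewer than 2 patients. With 6 patients, 1/6 = 16.7% passes and 2/6 = 33.3% does not. The two statements agree, and the rule works on counts within a cohort.

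**2. What each column contains** (cohort table in SAP 7.1, doses in ng/kg):

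| Column | Cohorts | Distinct levels or regimens | Span of fixed or Target dose |
|---|---|---|---|
| Fixed IV | 12 | 12 | 1.3 to 160; 160/1.3 = 123-fold |
| 1 Prime Step IV | 3 | 3: 12/36, 100/300, 75/225 | 36 to 300; 300/36 = 8.3-fold |
| 2 Prime Step IV | 4 | 3: 100/300/450, 50/150/300 (twice), 50/150/450 | 300 to 450; 450/300 = 1.5-fold |
| Fixed SC | 1 | 1 | single level |

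Cohorts: 12 + 3 + 4 + 1 = 20. Distinct levels or regimens: 12 + 3 + 3 + 1 = 19, because cohorts 502 and 503 share 50/150/300 and differ only by prior chemotherapy. The Step arm has 7 cohorts and 3 + 3 = 6 regimens in 2 columns.

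**3. Target Dose does not identify a Step regimen.** The 6 regimens use 4 Target Doses: 36, 225, 300 and 450. Target 300 follows a prime of 100 (cohort 301) and primes of 50 and 150 (502, 503). Target 450 follows 100 and 300 (501) and 50 and 150 (504), and both of these sit in the same column.

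**4. What a column entry can conceal.** Cohort sizes and DLT counts are not in the documents. As an illustration, assume 6 patients per cohort, all evaluable.

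- Pattern A: two DLT patients in one cohort, none elsewhere.
- Pattern B: one DLT patient in each of two cohorts.
- The one-prime column (3 cohorts) reads 2/(3 × 6) = 2/18 = 11.1% under both patterns.
- The two-prime column (4 cohorts) reads 2/(4 × 6) = 2/24 = 8.3% under both.

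Under A, one cohort has passed the MTD by the count rule; under B, none has. The table gives the same entry. With 3 per cohort, pattern A would read 2/9 = 22.2% or 2/12 = 16.7%. Backfill (Protocol 3.1.1.4) could make the denominators larger.

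**5. Denominator.** Two DLT patients among 6 evaluable is 33%. If 1 or 2 replaced patients are also counted, it shows as 2/7 = 29% or 2/8 = 25%. The 3+3 decision is unchanged because it rests on the count, but the displayed proportion is not the one the MTD definition names.

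**6. Which text governs.** SAP 7.1 applies to all safety tables and describes its four headers as the way the dosing cohorts are presented. Read that way, the word cohort in 10.2 can mean those columns. The word *generally* in 7.1 and the sentence in 6.3 leave room for the other reading. The SAP does not settle it.

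**The case against.** The best defence is that SAP 6.3 and 10.2 already promise summaries by cohort, that 7.1 only says tables will generally use the grouping, and that a per-cohort listing exists. Protocol 10.7 asks for DLTs to be listed separately and summarised, without specifying columns, and the SAP does both. The trial was discontinued on 10 March 2022, and a short synoptic report may reasonably group sparse cohorts. This makes the defect an unresolved inconsistency rather than a certain loss. It does not remove the defect, because nothing in the SAP says that the DLT table departs from the 7.1 headers. The space argument is also weak for a DLT table of about 20 rows.

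Four stronger readings are tempting, and the documents do not support them.

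- *Pooling could hide a breach of the MTD.* A reader might set a pooled percentage against the 33% limit. No decision uses column percentages. Protocol 3.1.1 and 11.9 have the Cohort Review Committee review each cohort as it completes, and the rule is a count.
- *The Step MTD is undefined because Protocol 3.1.1.2 names only the Target Dose.* Table 8, 3.1.1.2.2 and 3.1.2 all treat Step tolerability as a property of the priming and Target regimen. Only the label used in the report needs care.
- *The intrapatient ceiling in Protocol 3.1.1.5 could take an unprimed patient to a dose cleared only after priming.* No document says that 450 ng/kg was cleared or that any such patient was escalated. The section requires 6 prior doses, Medical Monitor approval and a 24-hour admission, and the trial has stopped.
- *"Patients will be reported in their original dose cohort, regardless of any intra-patient dose escalation or dose changes", so DLTs at an escalated dose would be credited to a lower cohort.* The DLT window is 21 days from the first Target Dose. Six weekly doses put the first escalated dose about 6 × 7 = 42 days after the first dose at that level, outside the window. Only late DLTs, followed to day 60, could overlap.

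**Conclusion.** The concern holds as a minor reporting point. As SAP 7.1 reads, the one retained primary endpoint is tabulated with 19 dose levels or regimens in 4 columns. Twelve Fixed IV levels over a 123-fold range are in one column and 6 Step regimens are in two. A display by dose level or regimen is certain only in listing 16.2.7.3, without denominators. The counts come straight from the SAP cohort table and need no assumption. The illustration in step 4 assumes cohort sizes, and whether pooling conceals any actual pattern cannot be known from the documents. Dose decisions during the trial are not affected.

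**What to change.** Exempt the DLT summary from the 7.1 grouping, or add one table to the synoptic report. It would have a row for each of the 20 cohorts, showing:

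- the regimen, as priming sequence and Target Dose where relevant;
- patients with a DLT over patients treated;
- patients with a DLT over DLT-evaluable patients, meaning those with 3 or more Target doses or a DLT;
- maximum DLT grade.

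Show cohorts 502 and 503 separately and combined, which makes 20 + 1 = 21 rows. Footnote any patient whose evaluability was judged differently by the Cohort Review Committee, since Protocol 5.2 leaves some discretion. State any Step MTD or MAD as priming sequence plus Target Dose. Add one sentence to SAP 10.2 saying what cohort means there.

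The cost is one descriptive table from data already collected, with evaluability checked against committee records. The drawback is sparse rows, often 3 to 6 patients, so counts should lead and percentages be read with care. No protocol change is needed.
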